## **Clinical Study Protocol** **Johnson & Johnson Vision**

**Note:** This definition includes events related to the investigational medical device or the comparator, and to the procedures involved. For users or other persons, this definition is restricted to events related to investigational medical devices.

An AE includes any condition (including a pre-existing condition) that:

1. Was not present prior to the study, but appeared or reappeared following initiation of the study.
2. Was present prior to the study but worsened during the study. This would include any condition resulting from concomitant illnesses, reactions to concomitant medications, or progression of disease states.

**Note:** Pregnancy must be documented as an adverse event and must be reported to the clinical monitor and to the Sponsor immediately upon learning of the event.

**Serious Adverse Event (SAE)** – An SAE is any adverse event that led to any of the following:

- Death
- Serious deterioration in the health of the subject that resulted in any of the following:
- Life-threatening illness or injury
- Permanent or persistent impairment of a body structure or a body function
- Hospitalization or prolongation of patient hospitalization
- Medical or surgical intervention to prevent life-threatening illness or injury or permanent impairment to a body structure or a body function.
- Chronic disease
- Fetal distress, fetal death or a congenital physical or mental impairment of birth defect.

Diagnoses and conditions that are considered Ocular Serious Adverse Events include, but not limited to:

- Microbial Keratitis (MK)
- Iritis (including cells in the anterior chamber)
- Permanent decrease in best spectacle corrected visual acuity equivalent to 2 acuity lines or greater
- Central Corneal Opacity
- Central Corneal Neovascularization
- Uveitis
- Endophthalmitis
- Hypopyon
- Hyphemia
- Penetration of Bowman's Membrane
- Persistent Epithelial Defect
- Limbal cell Damage leading to Conjunctivalization

## **Clinical Study Protocol** **Johnson & Johnson Vision**

**Significant Adverse Events** – are defined as events that are symptomatic and warrant discontinuation (temporary or permanent) of the contact lens wear

Diagnoses and conditions that are considered Ocular Significant Adverse Events include, but not limited to the following:

- Contact Lens Induced Peripheral Ulcer (CLPU)
- Significant Infiltrative Events (SIE)
- Superior Epithelial Arcuate Lesions (SEALs)
- Any Temporary Loss of > 2 Lines of BSCVA
- Other grade 3 or higher corneal findings, such as abrasions or edema
- Non-contact lens related corneal events - e.g. Epidemic Keratoconjunctivitis (EKC)
- Asymptomatic Corneal Scar
- Any corneal event which necessitates temporary lens discontinuation > 2 weeks

**Non-Significant Adverse Events** – are defined as those events that are usually asymptomatic and usually do not warrant discontinuation of contact lens wear but may cause a reduction in wear time. However, the Investigator may choose to prescribe treatment as a precautionary measure.

Diagnoses and conditions that are considered Ocular Non-Significant Adverse Events include, but not limited to the following:

- Non-significant Infiltrative Event (NSIE)
- Contact Lens Papillary Conjunctivitis (CLPC)
- Superficial Punctate Keratitis (SPK)
- Conjunctivitis: Bacterial, Viral, Allergic
- Blepharitis
- Meibomianitis
- Contact Dermatitis
- Localized Allergic Reactions
- Any corneal event not explicitly defined as serious or significant adverse event, which necessitates temporary lens discontinuation < 2 weeks

**Adverse Device Effect (ADE)** – An ADE is an “adverse event related to the use of an investigational medical device.”

**NOTE 1: This definition includes adverse events resulting from insufficient or inadequate instructions for use, deployment, implantation, installation, or operation, or any malfunction of the investigational medical device.**

**NOTE 2: This definition includes any event resulting from use error or from intentional misuse of the investigational medical device.**

**Unanticipated Adverse Device Effect (UADE)** – A UADE is any serious adverse effect on health or safety or any life-threatening problem or death caused by, or associated with, the test

# **Clinical Study Protocol**

## **Johnson & Johnson Vision**

article, if that effect, problem, or death was not previously identified in nature, severity, or degree of incidence in the investigational plan, Investigator's Brochure or protocol, or any other unanticipated serious problem associated with the test article that relates to the rights, safety and welfare of subjects.

### **13.2. Assessing Adverse Events**

In conjunction with the medical monitor, the Investigator will evaluate adverse events to ensure the events are categorized correctly. Elements of categorization will include:

- Seriousness/Classifications (see definition in section 13.1).
- Causality or Relatedness – i.e., the relationship between the test article, study treatment or study procedures and the adverse event (not related, unlikely related, possibly related, or related - see definition in section 13.2.1).
- Adverse Event Severity – Adverse event severity is used to assess the degree of intensity of the adverse event (mild, moderate, or severe - see definition in section 13.2.2).
- Outcome – not recovered or not resolved, recovering or resolving, recovered or resolved with sequelae, recovered or resolved, death related to adverse event, or unknown.
- Actions Taken – none, temporarily discontinued, permanently discontinued, or other.

#### **13.2.1. Causality Assessment**

**Causality Assessment** – A determination of the relationship between an adverse event and the test article. The test article relationship for each adverse event should be determined by the investigator using these explanations:

- Not Related- An adverse event that is not related to the use of the test article, study treatment or study procedures.
- Unlikely Related – An adverse event for which an alternative explanation is more likely, e.g. concomitant treatment, concomitant disease(s), or the relationship of time suggests that a causal relationship is not likely.
- Possibly Related – An adverse event that might be due to the use of the test article, or to the study treatment or study procedures. An alternative explanation, e.g. concomitant treatment, concomitant disease(s), is inconclusive. The relationship in time is reasonable. Therefore, the causal relationship cannot be excluded.
- Related – An adverse event that is listed as a possible adverse effect (device) or adverse reaction (drug) and cannot be reasonably explained by an alternative explanation, e.g. concomitant treatment of concomitant disease(s). The relationship in time is very suggestive, e.g. it is confirmed by de-challenge and re-challenge.

#### **13.2.2. Severity Assessment**

**Severity Assessment** – A qualitative assessment of the degree of intensity of an adverse event as determined by the Investigator or reported to him/her by the subject. The assessment of severity is made irrespective of test article, study treatment or study procedure relationship or seriousness of the event and should be evaluated according to the following scale:

# **Clinical Study Protocol**

## **Johnson & Johnson Vision**

- Mild – Event is noticeable to the subject but is easily tolerated and does not interfere with the subject’s daily activities.
- Moderate – Event is bothersome, possible requiring additional therapy, and may interfere with the subject’s daily activities.
- Severe – Event is intolerable, necessitates additional therapy or alteration of therapy and interferes with the subject’s daily activities.

### **13.3. Documentation and Follow-Up of Adverse Events**

The recording and documenting of adverse events (ocular and non-ocular) begin when the subjects are exposed to the test article, study treatment or study procedure. Adverse events reported before the use of test article, start of study treatment, or study procedures will be recorded as medical history. However, if the condition deteriorates at any time during the study it will be recorded and reported as an AE. Untoward medical events reported after the subject’s exit from the study will be recorded as adverse events at the discretion of the Investigator.

Upon finding an adverse event, the Principal Investigator will document the condition in the subject record and in the eCRFs and complete the Adverse Event eCRF.

Complete descriptions of all adverse events must be available in the subject record. All Adverse Events including local and systemic reactions not meeting the criteria for “serious adverse events” shall be captured on the appropriate case report form or electronic data system. All adverse events occurring while the subject is enrolled in the study must be documented appropriately regardless of relationship.

It is the Investigator’s responsibility to maintain documentation of each reported adverse event. All adverse events will be followed in accordance with applicable licensing requirements. Such documentation will include the following:

- Adverse event (diagnosis not symptom).
- Drawings or photographs (where appropriate) that detail the finding (e.g., size, location, and depth, etc.).
- Date the clinical site was notified.
- Date and time of onset.
- Date and time of resolution.
- Adverse event classification, severity, and relationship to test articles, as applicable.
- Treatment regimen instituted (where appropriate), including concomitant medications prescribed, in accordance with applicable licensing requirements.
- Any referral to another health care provider if needed.
- Outcome, ocular damage (if any).
- Likely etiology.
- Best corrected visual acuity at the discovery of the event and upon conclusion of the event, if the AE is related to the visual system.

# **Clinical Study Protocol**

## **Johnson & Johnson Vision**

Upon discovery of an AE that is deemed ‘possibly related’ or ‘related’ to the test article or study procedures (whether related to the visual system or not), an AE review form [REDACTED] must be completed. Additional dated and initialed entries should be made at follow-up evaluations. Separate forms must be completed for each eye if the AE is bilateral.

In addition, if an infiltrate(s) is present, he/she will complete the Corneal Infiltrate Assessment eCRF. Where necessary, a culture of the corneal lesion will be collected to determine if the infection is microbial in nature. If cultures are collected, the date of culture collection and laboratory utilized will be recorded.

Changes in the severity of an AE shall be documented to allow an assessment of the duration of the event at each level of intensity to be performed. Adverse events characterized as intermittent require documentation of the onset and duration of each episode. Changes in the assessment of relationship to the Test Article shall also be clearly documented.

Subjects who present with an adverse event shall be followed by the Investigator, within licensure, until all signs and symptoms have returned to pre-treatment status, stabilized, or been satisfactorily resolved. If further treatment beyond licensure is required, the patient will be referred to the appropriate health care provider. The Investigator will use his/her clinical judgment as to whether a subject reporting with an adverse event will continue in the study. If a subject is discontinued from the study, it will be the responsibility of the Investigator to record the reason for discontinuation. The Investigator will also document the adverse event appropriately and complete the Adverse Event eCRF. Any subjects with ongoing adverse events related to the test article, study treatment or study procedures, as of the final study visit date, should be followed to resolution of the adverse event or until referral to an appropriate health care provider, as recommended by the Investigator. Non-ocular adverse events that are not related to the test article, study treatment, or study procedures may be recorded as “ongoing” without further follow-up.

### **13.4. Reporting Adverse Events**

The Investigator will notify the Sponsor of an adverse event by e-mail, facsimile, or telephone as soon as possible and no later than 24 hours from discovery for any serious /significant adverse events, and 2 days from discovery for any non-significant adverse event. In addition, a written report will be submitted by the Principal Investigator to the IEC/IRB according to their requirements (section 13.4.2). The report will comment whether the adverse event was considered to be related to the test article, study treatment or study procedures.

#### **13.4.1. Reporting Adverse Events to Sponsor**

##### **Serious/Significant Adverse Events**

The Investigator will inform the sponsor of all serious/significant adverse events occurring during the study period as soon as possible by e-mail or telephone, but no later than 24 hours following discovery of the event. The Investigator is obligated to pursue and obtain information requested by the Sponsor in addition to that information reported on the eCRF. All subjects experiencing a serious/significant adverse event must be followed up and all outcomes must be reported.

## **Clinical Study Protocol Johnson & Johnson Vision**

When medically necessary, the Investigator may break the randomization code to determine the identity of the treatment that the subject received. The Sponsor and study monitor should be notified prior to unmasking the test articles.

In the event of a serious/significant adverse event, the Investigator must:

- Notify the Sponsor immediately.
- Obtain and maintain in the subject's records all pertinent medical information and medical judgment for colleagues who assisted in the treatment and follow-up of the subject.
- Provide the Sponsor with a complete case history which includes a statement as to whether the event was or was not related to the use of the test article.
- Notify the IEC/IRB as required by the IEC/IRB reporting procedure according to national regulations.

### **Unanticipated (Serious) Adverse Device Effect (UADE)**

In the event of an Unanticipated (Serious) Adverse Device Effect (UADE), the Investigator will submit a report of the UADE to the Sponsor and IEC/IRB as soon as possible, but no later than 24 hours after the Investigator first learns of the effect. This report is in addition to the immediate notification mentioned above.

The Sponsor must conduct an evaluation of the UADE and must report the results of the evaluation to FDA, the IEC/IRB and participating Investigators within 10 working days after the Sponsor first receives notification of the effect.

### **Non-Serious Adverse Events**

All non-serious adverse events, including non-serious adverse device effects, will be reported to the sponsor by the Investigator no later than 2 days from discovery.

#### **13.4.2. Reporting Adverse Events to the Responsible IEC/IRB and Health Authorities**

Adverse events that meet the IEC/IRB requirements for reporting must be reported within the IEC/IRB's written guidelines. Each clinical site will refer to and follow any guidelines set forth by their Approving IEC/IRB. Each clinical site will refer to and follow any guidelines set forth by their local governing Health Authorities.

The Sponsor will report applicable Adverse Events to the local health authorities according to the written guidelines, including reporting timelines.

#### **13.5. Event of Special Interest**

None

# **Clinical Study Protocol**

## **Johnson & Johnson Vision**

### **13.6. Reporting of Pregnancy**

Subjects reporting pregnancy (by self-report) during the study will be discontinued after the event is recorded as an Adverse Event. Once discontinued, pregnant participants and their fetuses will not be monitored for study related purposes. Pregnant participants are not discontinued from contact lens or solution related studies for safety concerns, but due to general concerns relating to pregnancy and contact lens use. Specifically, pregnant women are discontinued due to fluctuations in refractive error and/or visual acuity that occur secondary to systemic hormonal changes, and not due to unforeseen health risks to the mother or fetus.

## **14. STATISTICAL METHODS**

### **14.1. General Considerations**

Statistical Analysis will be undertaken by the sponsor or under the authority of the sponsor. A general description of the statistical methods to be implemented in this clinical trial is outlined below.

All data summaries and statistical analyses will be performed using the Statistical Analysis System (SAS) software Version 9.4 or higher (SAS Institute, Cary, NC). Throughout the analysis of data, the results for each subject/eye will be used when available for summarization and statistical analysis. Unscheduled visits will be summarized separately and will be excluded from the statistical analysis.

Summary tables (descriptive statistics and/or frequency tables) will be provided for all baseline variables, efficacy variables and safety variables as appropriate. Continuous variables will be summarized with descriptive statistics (n, mean, standard deviation [SD], median, minimum and maximum). Frequency count and percentage of subjects or eyes within each category will be provided for categorical data.

Summaries will be presented separately for each phase and lens type (Test and Control) and will be performed separately by completion status (Safety Population, Per-Protocol Population and Intent-to-Treat Population, when appropriate).

### **14.2. Sample Size Justification**

Sample size for Phase 1 was not determined on the basis of statistical considerations because it is primarily for the collecting clinical data to calculate the required sample size for Phase 2.

Sample size requirements for Phase 2 were based on assumptions derived from the analysis of selected data collected in Phase 1. It was calculated that the total sample size of 120 subjects to complete (40 per group) the study provides at least 90% power to test each primary and secondary hypothesis. The sample size and power calculations were performed using a paired sample *t*-test approach (exact method) in PASS (NCSS, 2021).

A gate-keeping approach will be used to control the study-wise Type I error rate at the one-sided 0.025 level and adjust for multiplicity due to multiple efficacy endpoints of interest in combination of Bonferroni adjustment. The null hypothesis for the primary efficacy endpoints has to be rejected at one-sided alpha level of 0.025 first, in order to propagate the full alpha to the secondary family of hypothesis tests. The Bonferroni approach will apply then to testing the secondary efficacy endpoints.

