# **Clinical Study Protocol**

## **Johnson & Johnson Vision**

Sample Size	
Phase 1 will pilot the procedures and will enroll approximately 24 subjects, with a target of at least 20 to complete (~10 spherical wearers and ~10 multifocal wearers). Data from Phase 1 will be used for sample size estimation for Phase 2. Subjects in Phase 1 will not participate in Phase 2.
 
Phase 2 will execute the same procedures as Phase 1 with a different sample size. Phase 2 sample size will be calculated based on data collected from Phase 1. The total sample size for Phase 2 will be approximately 135 subjects (45 per subject group to enroll and 40 to complete) due to resources and study timing.

Study Duration	
There are two study visits in each phase that will last approximately 2.5-3 hours each and will be separated by 1-14 days.
 

• The study enrollment period for Phase 1 will be approximately 2 weeks, making the duration of Phase 1 approximately 4 weeks.

• Up to 2 weeks will be allotted for statistical analyses.

• The study enrollment period for Phase 2 will be approximately 12 weeks, making the duration of Phase 2 approximately 14 weeks.

• The total study duration is expected to last about 20 weeks.

Anticipated Study Population	
All subjects will be healthy adult male and female volunteers of any race and ethnicity that satisfy the inclusion criteria. All subjects must habitually wear one of three soft contact lenses within the power ranges available for this study:
 

1. Spherical

2. Multifocal

3. Toric (astigmatism)

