# Clinical Study Protocol

## Johnson & Johnson Vision

The sample size estimates for primary endpoints were calculated using 1-sided Type I error rate of 0.025 for each endpoint. The sample size estimates for the two secondary endpoints were adjusted using a Bonferroni adjustment and calculated using a one-sided Type I error rate of 0.0125 (i.e., one-sided 0.025/2).

While no Toric wearers were enrolled in Phase 1, it is anticipated that the multifocal group would require the largest sample due to simultaneous optics of the multifocal lens and the intraocular scattering that naturally occurs with age, which can both compromise and reduce the quality of vision. Hence it is expected that the sample size required to test endpoints for Toric wearers would be no more than the sample size required for Multifocal wearers. As these endpoints did not have data from Phase 1, all hypotheses for the Toric wearers will be exploratory endpoints.

Table 9 displays the statistical power and associated sample sizes estimates derived for the primary and secondary endpoints for Sphere and Multifocal groups, given the assumed treatment effect sizes. Based on the table below, it is planned that Phase 2 will enroll approximately 135 subjects (45 subjects per group) with the target of 120 subjects (40 subjects per group) to complete the study, assuming approximately a 10% drop-out rate.

Table 9: Assumptions for Power and Sample Size Calculations for The Primary and Secondary Endpoints

Endpoint Type	Endpoint (Subject Group)	Standard Deviation of Paired Differences	Effect Size	Alpha	Power	Sample Size Per Group
Primary	Visual Range (Sphere)	0.10	1.83	0.05	0.94	6
	Visual Range (Multifocal)	0.23	0.52	0.05	0.90	41
Secondary	Motion Detection (Sphere)	1.16	0.99	0.03	0.92	16
	Brightness Perception (Multifocal)	0.20	0.70	0.03	0.91	29

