# Clinical Study Protocol

## Johnson & Johnson Vision

### 14.4. Level of Statistical Significance

Although the Test and Control lenses are senofilcon A based lenses with and without the new UV/HEV filter, respectively, the study lenses assigned to each subject group will be different with different optical designs specifically for vision correction of the sphere, multifocal, and toric (astigmatism) lens wearers. Therefore, the planned hypotheses in Phase 2 will be tested separately for each subject group without Type I error adjustment across the three subject groups, due to different optical designs of the study lenses for different groups. The primary hypothesis for each subject group will be tested using a one-sided Type I error rate of 0.025. The secondary hypotheses will be tested only when the primary hypothesis is met for the same subject group. For secondary hypotheses, the Type I error rate will be adjusted using the Bonferroni approach for the two secondary hypotheses and each secondary hypothesis will be tested using the Bonferroni adjusted one-sided Type I error rate 0.0125 (i.e., one-sided 0.025/2).

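### Section 14.2 states at least 90% power for every hypothesis at 40 completers per group, but Table 9 requires 41 for multifocal visual range, and power at 40 is 0.894

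*Combined protocol and SAP*

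**What the plan says.** Section 14.2 gives the Phase 2 size as "the total sample size of 120 subjects to complete (40 per group") and says that with this number "the study provides at least 90% power to test each primary and secondary hypothesis". The calculations were "performed using a paired sample *t*-test approach (exact method) in PASS". On alpha it says: "The sample size estimates for primary endpoints were calculated using 1-sided Type I error rate of 0.025 for each endpoint". The two secondary endpoints were "calculated using a one-sided Type I error rate of 0.0125 (i.e., one-sided 0.025/2").

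Table 9 then gives one row per hypothesis. The row for visual range in multifocal wearers shows a standard deviation of paired differences of 0.23, an effect size of 0.52, power of 0.90 and a sample size of 41. The other rows need 6, 16 and 29.

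The paragraph that introduces the table refers to it as the basis for the plan and sets a "target of 120 subjects (40 subjects per group) to complete the study", allowing for about 10% drop-out. The Synopsis has the same numbers: "45 per subject group to enroll and 40 to complete".

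Section 14.4 adds a gate: "The secondary hypotheses will be tested only when the primary hypothesis is met for the same subject group".

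**The concern.** The text and the table in one section disagree. The text promises 90% or more for each hypothesis at 40 completers, while the table says one primary hypothesis needs 41 to reach 0.90. Multifocal visual range has the largest requirement of the four rows, so it is the row on which the statistical case for 40 per group rests. Section 14.2 also sizes the toric group by reference to what the multifocal group needs.

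The brightness test in multifocal wearers is run only if multifocal visual range succeeds. A reader who takes the 90% statement at face value will therefore also be slightly too optimistic about reaching that secondary claim. Section 2.1 says the results may support marketing claims, so the stated power should agree with the plan's own table.

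**Working it through.** **Inputs.** Effect sizes d and sample sizes come from Table 9. The method (exact paired t) and the one-sided alphas (0.025 primary, 0.0125 secondary) come from the text of Section 14.2. Table 9 prints alpha as 0.05 and 0.03, which fit as the two-sided equivalents (2 × 0.025 = 0.05; 2 × 0.0125 = 0.025, rounded to 0.03).

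**Formula.** Power = P(T > t_crit), where T is noncentral t with n − 1 degrees of freedom and noncentrality d√n, and t_crit is the upper one-sided alpha point of the central t with n − 1 degrees of freedom.

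**Step 1: reproduce Table 9, then move each row to 40.**

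| Hypothesis | d | One-sided alpha | Table 9 n | Table 9 power | Recomputed at Table 9 n | Power at n = 40 |
|---|---|---|---|---|---|---|
| Visual range, sphere | 1.83 | 0.025 | 6 | 0.94 | 0.9425 | >0.999 |
| Visual range, multifocal | 0.52 | 0.025 | 41 | 0.90 | 0.9013 | **0.8938** |
| Motion detection, sphere | 0.99 | 0.0125 | 16 | 0.92 | 0.9156 | 0.9999 |
| Brightness, multifocal | 0.70 | 0.0125 | 29 | 0.91 | 0.9124 | 0.9793 |

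All four printed powers are recovered, so the method and alphas are the ones the sponsor used.

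**Step 2: the multifocal visual range row in detail.**
- n = 41: noncentrality 0.52 × √41 = 3.330, critical value 2.021 on 40 degrees of freedom, power 0.9013.
- n = 40: noncentrality 0.52 × √40 = 3.289, critical value 2.023 on 39 degrees of freedom, power 0.8938.
- The shortfall is 0.90 − 0.894 = 0.006. With d = 0.52, 41 is the smallest n that reaches 0.90.

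**Step 3: could another reading rescue the statement?**
- *Rounding of d.* At n = 40, power is 0.888 for d = 0.515 and 0.899 for d just under 0.525. Power of 0.90 at n = 40 needs d = 0.5256, which would print as 0.53.
- *One-sided alpha of 0.05.* This gives 0.948 at n = 41, which does not match the printed 0.90.
- *Normal approximation.* This gives 0.908 at n = 40, but it would have required only 39 subjects, not the printed 41, and it is not the declared exact method.
- *n − 2 degrees of freedom*, to allow for a period term. Power is 0.893 at 40 and 0.901 at 41.

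**Step 4: enrolment.** At 10% drop-out, 45 enrolled gives 45 × 0.9 = 40.5 expected completers. For 41 completers, 41 / 0.9 = 45.6, so 46 would be enrolled.

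**Step 5: effect of the gate on brightness.** The chance that both multifocal tests succeed is at most 0.894, the smaller of the two powers, and at least 0.8938 + 0.9793 − 1 = 0.873, whatever the dependence between them. If the endpoints were independent, which is an assumption, it would be 0.8938 × 0.9793 = 0.875.

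**The case against.** The strongest reply is that the gap is trivial. It is one completer, no decision rule depends on it, Table 9 openly prints the 41, and Section 14.8 asks only for 80% power on the primary hypothesis in each group, which 0.894 exceeds. The effect size also comes from about 10 multifocal subjects in Phase 1. A rough 95% interval for d = 0.52 at n = 10 (normal approximation) runs from about −0.14 to 1.18, so the difference between 0.894 and 0.90 is far inside the uncertainty. The Synopsis and Section 4.3 add that the Phase 2 total was set partly by resources and timing. All of this is right, and it bears on how much the error matters. It does not make the 90% sentence true.

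A second reply is that the primary analysis is a mixed model on all randomized subjects, so someone who leaves after the first period still contributes. As an illustration, assume 40 completers, five further subjects with period 1 only, equal variances and a within-subject correlation that the documents do not give. The information is then worth about 42.4 complete pairs at correlation 0 and 40.2 at correlation 0.9, with power from about 0.91 down to about 0.895. The true power of the planned analysis could therefore fall on either side of 0.90. That is a fair caveat on the 0.894, which is the paired-t figure. But Section 14.2 rests its statement on the paired t-test and on completers, and on that basis it fails.

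A third reply is that Section 14.2 makes a per-test claim, so the gated probability for brightness does not show an error in it. That stands: brightness on its own has 0.979. The gated figure is useful context only.

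**Conclusion.** The statement is wrong as written for one of the four hypotheses. At 40 completers, multifocal visual range has power 0.894 (0.888 to 0.899 over effect sizes that print as 0.52) against the stated minimum of 0.90. The other three hypotheses meet the claim per test. The conclusion rests on the plan's own inputs: the exact paired t-test, one-sided alpha 0.025, d = 0.52, and both periods analysed. This is a small internal inconsistency in the sample size justification. It should be corrected, but it does not threaten the trial's ability to answer its question.

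**What to change.** Replace the power sentence in Section 14.2 with, for example:

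> With 40 completers per group, per-test power by the paired t-test is about 89% for multifocal visual range, about 98% for multifocal brightness perception, and above 99% for both sphere endpoints.

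Optionally add that these figures assume data from both periods are analysed, since Section 14.5 falls back to period 1 alone after a significant sequence effect. It could also be noted that, because of the gate in Section 14.4, the overall chance of success on brightness is at most about 89% (about 87.5% if the two endpoints are independent, an assumption).

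This costs wording only: no extra subjects and no change to alpha, analysis or decision rules. The stated power for one hypothesis becomes slightly less favourable. Two alternatives would also reconcile text and table. One is to soften the claim to approximately 90%. The other is to keep the claim and raise the multifocal target to 41 completers, or 46 enrolled at 10% drop-out, which is one more than planned.
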